1.3.2. Part B: Multiple-Ascending Dose of LY3872386 in Patients with Atopic Dermatitis

1.3.2.1. Part B: LY3872386 CC Dosing Schedule

1.3.2.1. Part B	5: LY38/23	00 CC		D. 4 D. I		osing S				1 .				
Procedures/ Assessments	Screening		 	Part B: I Treat	ment Po			Do	osing Sch	Follo	w-up		ED	Comments
Visit Number	V1	V2	V3	V4	V5	V6	V7	V8	V 801	V 802	V 803	V 804		
Study Day(s)	CC													
Informed consent	X													
Review/confirm I/E criteria	X	P												
IWRS randomization		P												
Clinical Assessments														
Complete medical history	X													
Review preexisting conditions/AEs	X	P	P	P	P	P	P	P	X	X	X	X	X	
Concomitant medications	X	P	P	P	P	P	P	P	X	X	X	X	X	
Previous and current AD treatments	X													
Substance use (alcohol and tobacco use)	X													
Physical examination	X			X		X		X	X	X	X	X	X	
Weight	X											X	X	
Height	X													
Vital signs	X	P	P	P	P	P	P	P	X	X	X	X	X	
ECGs	X	P	P	P	P	P	P	P				X	X	

]	Part B: I	LY38723	886 CCI		De	osing Sch	nedule				
Procedures/ Assessments	Screening			Treat	tment Pe	eriod				Follo	w-up		ED	Comments
Visit Number	V1	V2	V3	V4	V5	V6	V7	V8	V	V	V	V		
									801	802	803	804		
Study Day(s)	CC													
Chest x-ray, if indicated (posterior-anterior view)	X													
IP administration		X	X	X	X	X	X	X						
QuantiFERON®-TB Gold test or TST	X													
vIGA-AD	X	X	X	X	X	X	X	X		X	X	X	X	
EASI	X	X	X	X	X	X	X	X		X	X	X	X	-
SCORAD	X	X	X	X	X	X	X	X		X	X	X	X	
POEM	X	X		X		X		X		X	X	X	X	
DLQI	X	X		X		X		X		X	X	X	X	
Itch numeric rating scale	X	X	X	X	X	X	X	X		X	X	X	X	
Laboratory Assessme	ents													
Beta-D-glucan	X													
Serologies, syphilis, and FSH	X													
Thyroid-stimulating hormone, including T3/T4 tests		P						X				X	X	
Serum immunoglobulins		X		X		X		X					X	

			I	Part B: I	LY38723	86 CC		Do	sing Sch	nedule				
Procedures/ Assessments	Screening			Treat	tment Pe	eriod				Follo	w-up		ED	Comments
Visit Number	V1	V2	V3	V4	V5	V6	V7	V8	V 801	V 802	V 803	V 804		
Study Day(s)	CC													
Subcutaneous local injection-site assessment		P	X	X	X	X	X	X		X	X	X	X	
Urinary drug screen (including ethanol breath test)	X	X	X	X	X	X	X	X						
Pregnancy test	X	P	P	P	P	P	P	P				X	X	
Clinical chemistry	X	X	X	X	X	X	X	X	X	X	X	X	X	
Fasting lipid panel		P		P		P			X				X	
Hematology	X	X	X	X	X	X	X	X	X	X	X	X	X	-
Hemoglobin A1c	X	X		X				X				X	X	
Urinalysis	X	X	X	X	X	X	X	X	X	X	X	X	X	-
Pharmacogenetics		P												-

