2.3. Benefit/Risk Assessment

The toxicology data for LY3872386 demonstrate an acceptable nonclinical safety profile and margin of safety to support the transition from preclinical status to a clinical single-dose study in healthy participants and a multiple-dose study in patients with AD.

The nonclinical safety profile of LY3872386 is generally consistent with its intended pharmacology. Primary safety concerns predicted from studies with the ADC and the payload are bacterial and other infections, secondary to decreases in lymphoid tissue lymphocytes and circulating blood lymphocytes. Other potential risks identified for LY3872386 in toxicology studies and consistent with GC pharmacology are

- atrophy of skin hair follicles, especially near SC injection sites, potentially leading to thinning hair or hair loss
- suppression of the HPA axis
- increased serum triglycerides, and
- increased serum glucose.

The safety and efficacy associated with modulation of the IL-4/IL-13/IL-4R axis have been evaluated with approved drugs such as dupilumab and tralokinumab, and the safety and efficacy of GCs as a class are well-established. The key safety concerns and PD effects of LY3872386, including infection, conjunctivitis, hypersensitivity reactions, local injection site reactions, and systemic GC exposure from LY3558533 (free payload), will be closely monitored during the clinical study.

As with other immunomodulatory therapies, LY3872386 and prednisone may increase the risk of developing infections, increase the risk of an infection becoming more serious, and/or change the effectiveness of vaccines administered. LY3872386 may also increase the risk of opportunistic infections and the reactivation of latent infections. Participants will therefore be screened for hepatitis B, hepatitis C, HIV, and TB. In addition, all participants should be monitored for symptoms and signs of infection after administration of LY3872386 or prednisone.

Infusion reactions and hypersensitivity reactions are potential risks for all biologics. These risks will be carefully monitored during the dosing period in Parts A and B (the LY3872386 portions of the study), with close observation after infusion and stopping rules that prevent re-challenge of patients/participants with significant hypersensitivity reactions.

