5.2. Exclusion Criteria

Participants are excluded from the study if any of the following criteria apply:

- 15. women who are pregnant and/or lactating.
- 16. are investigative site personnel directly affiliated with this study and their immediate families. Immediate family is defined as a spouse, biological or legal guardian, child, or sibling.
- 17. are Lilly employees or are employees of a third-party organization involved with the study.
- 18. are currently enrolled in a clinical study involving an IP or any other type of medical research judged not to be scientifically or medically compatible with this study or have received any nonbiologic or biologic agent (such as monoclonal antibodies, including marketed drugs) within 30 days or 5 half-lives (whichever is longer) of randomization.
- 19. have a current or recent acute, active infection. For at least 30 days before screening and up to the randomization visit, participants must have no symptoms or signs of infection in the absence of any, anti-infective treatment.
- 20. have had any of the following types of infection within 3 months prior to the screening visit or develops any of these infections before the randomization visit:
 - Serious (requiring hospitalization or IV or equivalent oral antibiotic treatment, or both)
 - Opportunistic (as defined in Winthrop et al. 2015)
 Note: Herpes zoster is considered active and ongoing until all vesicles are dry and crusted over.
 - Chronic (duration of symptoms, signs, and/or treatment of 6 weeks or longer)
 - Recurring (including, but not limited to, herpes simplex, herpes zoster, and recurring cellulitis). Participants with only recurrent, mild, and uncomplicated orolabial herpes and/or genital herpes may be discussed with the sponsor's designated medical monitor and considered for enrollment if other study eligibility requirements are met.
 - Have syphilis, as shown by positive results for both rapid plasma reagin and Treponema pallidum hemagglutination tests.
- 21. have received live vaccine(s) (including attenuated live vaccines) or Bacillus Calmette-Guérin within 35 days of screening or intend to receive them during the study (non-live or inactivated vaccinations are allowed) or within 14 weeks after receiving the last dose of study intervention.

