- 27. had any malignancy within the past 5 years. Exceptions: successfully treated basal cell skin carcinoma or squamous cell skin carcinoma with no evidence of recurrence or metastatic disease within the 3 years prior to baseline.
- 28. current smoker using >10 cigarettes or other tobacco products per day and are unable/unwilling to stop smoking tobacco products while in the study unit and have a positive cotinine test.
- 29. are regular users of known drugs of abuse and/or have positive findings on urinary drug tests at screening, OR an average weekly alcohol intake that exceeds 21 units per week (males) or 14 units per week (females), OR are unwilling to stop alcohol consumption during study visits/time in the research unit (1 unit of alcohol = 12 oz or 360 mL of beer, 5 oz or 150 mL of wine, and 1.5 oz or 45 mL of distilled spirits).
- 30. are regular users of cannabis (legal or medical).
- 31. have received blood products within 6 months before screening or donated blood of more than 500 mL within the previous 30 days of study screening.
 - a. For Chinese participants:
 - i. Have donated blood of more than 400 mL within the previous 30 days of study screening.
- 32. have known hypogammaglobulinemia or a screening serum immunoglobulin G or immunoglobulin M below the reference range.

33. have a history of a primary immunodeficiency, splenectomy, or any underlying condition that predisposes the participant to infection that, in the opinion of the sponsor or investigator, poses an unacceptable risk to the participant.

- 34. have presence of significant uncontrolled cerebro-cardiovascular (for example, myocardial infarction, unstable angina, hypertension, moderate-to-severe [New York Heart Association Class III/IV] heart failure, or cerebrovascular accident), respiratory, hepatic, renal, gastrointestinal, endocrine, hematologic, neurologic or neuropsychiatric disorders, or abnormal laboratory values at screening that, in the opinion of the sponsor or investigator, pose an unacceptable risk to the participant if participating in the study or interfering with the interpretation of data.

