8.2.9. Immunological Status Assessments

WBC subpopulations (including, but not limited to, total B cells, total T cells, and NK cells) in blood samples collected at visits and times specified in the SoA (Section 1.3) will be measured using flow cytometry as part of immunophenotyping assessment in Parts A, B, and C. A maximum of 3 samples may be collected at additional time points during the study (as unscheduled samples) if warranted and agreed upon between both the investigator and sponsor. Instructions for the collection and handling of blood samples will be provided by the sponsor. The actual date and 24-hour clock time of each sampling will be recorded. Immunoglobulin samples will also be collected as specified in the SoA (Section 1.3) as part of safety assessment.

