Beta D-glucand	FSH ⁱ
Cortisol (serum, cosyntropin stim, and urine)	Thyroid-stimulating hormone (including T3/T4 tests) Syphilis test (including RPR and TPPA as
	appropriate) ^g

Abbreviations: DNA = deoxyribonucleic acid; ED = early discontinuation; FSH = follicle-stimulating hormone; HIV = human immunodeficiency virus; Ig = immunoglobulin; NK cell = natural killer cell; RBC = red blood cell; RPR = Rapid Plasma Regain; TPPA = Treponema Pallidium Particle Agglutination.

Note: Results of these assays will be validated by the local laboratory at the time of testing. Additional tests may be performed or auto calculated by the laboratory as part of its standard panel that cannot be removed. Some of the above parameters are calculated from measured values. The omission of calculated values will not be considered as a protocol violation.

- a To be done centrally. If needed for safety, site may also perform locally.
- b Test only if dipstick result is abnormal.
- ^c Urine drug screen and ethanol breath testing may be repeated prior to admission to the clinical research unit and at other times indicated in the Schedule of Activities. Unscheduled testing is allowed.
- d Evaluation of beta-D-glucan may be performed at a local laboratory. Beta-D-glucan is required at screening for Part B only (to be performed centrally), and if an investigator believes it is warranted, at subsequent visits (may be performed centrally or locally), a beta-D-glucan test may be included in the work up panel at any time during the study. If the beta-D-glucan test is positive, pneumocystis pneumonia (PCP) needs to be ruled out. If PCP is ruled out and the investigator deems the patient fit to continue, the patient may continue in the study. If a patient has a confirmed diagnosis of PCP during the study, the patient must discontinue the study.
- e Not performed at screening.
- f Bedside glucose monitoring is performed using standard glucose monitors and capillary blood taken from fingerstick. Fasting should be approximately 2 hours, at a minimum.
- g Performed at screening only.
- h These tests may be waived if performed within 6 months prior to screening, and if test results are available for "review" for hepatitis B, C, and HIV.
- i To be performed on all female participants.

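### Exclusion criterion 32 depends on a screening IgG/IgM result, but neither Part B schedule draws immunoglobulins before the visit of randomization and first dose

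*Protocol*

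**What the plan says.** Criterion 32 in Protocol Section 5.2 covers participants whose hypogammaglobulinemia is already known, and those with "a screening serum immunoglobulin G or immunoglobulin M below the reference range". Section 5.2 opens with "Participants are excluded from the study if any of the following criteria apply" and names no part. Section 5.2.1 lists further criteria for Part B and does not replace the general ones. Section 8 requires screening evaluations to be finished and reviewed to confirm every eligibility criterion, and Section 5 rules out waivers.

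No text section fixes the timing of the test. Section 8.2.9 states: "Immunoglobulin samples will also be collected as specified in the SoA (Section 1.3) as part of safety assessment". The schedule therefore decides.

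- Part A (Section 1.3.1) and both Part C schedules (1.3.3.1 and 1.3.3.2) mark serum immunoglobulins at screening and again predose on the first dosing day.
- In both Part B schedules (1.3.2.1 and 1.3.2.2) the row "Serum immunoglobulins" is empty at V1 and first marked at V2. The row "IWRS randomization" and the first administration of investigational product are also at V2.

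In Section 10.2, serum immunoglobulins carry the footnote "To be done centrally. If needed for safety, site may also perform locally". The same section lets screening assessments go to the local laboratory in Parts A and C, not in Part B.

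**The concern.** An exclusion rule works only if its input exists when eligibility is decided. In Part B the rule asks for a screening value that the schedule does not produce. A patient with unrecognized low IgG or IgM could be randomized and dosed before anyone sees the result.

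Part B is where this matters most. It alone gives LY3872386 repeatedly, for up to 12 weeks. Section 2.3 names as the primary predicted safety concern "bacterial and other infections, secondary to decreases in lymphoid tissue lymphocytes and circulating blood lymphocytes". Part B also adds a beta-D-glucan test at screening, so the plan evidently meant infection risk to be screened more closely there. Yet the immunoglobulin check is scheduled for single-dose healthy participants and not for repeat-dosed patients.

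There is also a consequence for the data. Adverse events are the primary endpoint, and the safety set keeps everyone who received at least one dose (Protocol Section 9.2; SAP Section 9). An infection in a patient who should have been excluded would stay in that summary.

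**Working it through.** **1. Immunoglobulin row across the five schedules.** The last column is the number of samples with immunoglobulins listed in the blood-sampling tables (Section 10.2.1).

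| Schedule | Screening | Marks after screening, before early discontinuation (ED) | Count | Blood table |
|---|---|---|---|---|
| Part A, 1.3.1 | marked | Day 1 predose, last inpatient day, V802, V804, V806, V808 | 6 | 6 |
| Part B, 1.3.2.1 | blank | V2, V4, V6, V8 | 4 | 4 |
| Part B, 1.3.2.2 | blank | V2, V4, V6, V8 | 4 | 4 |
| Part C, 1.3.3.1 | marked | four | 4 | 4 |
| Part C, 1.3.3.2 | marked | four | 4 | 4 |

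The plan's Part B figure is reproduced: 4 samples × 8 mL = 32 mL in each Part B table.

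**2. Could the blank cell be a column shift from reading the PDF?** In Parts A and C the tabulated count equals the draws after screening, without ED. Screening blood sits in a separate 45 mL line. By that convention, the 4 samples in each Part B table are all post-screening draws. The second Part B row has exactly four marks in total, so none can be the screening cell. In the first Part B schedule the four marks plus ED account for the whole row.

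Other Part B rows map correctly as well:
- Thyroid tests have 3 draws from V2 predose onward in each schedule, and the tables list 3.
- Chemistry after screening and before ED has 11 draws in the first schedule (7 + 4 in the table) and 9 in the second (5 + 4).

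**3. Can the V2 sample stand in for screening?** It is drawn at the visit of randomization and first dose, is assigned to the central laboratory, and is marked X, not P, so the schedule does not require it to be predose. No turnaround time is given. That the result would normally arrive after dosing is an inference from these facts.

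**4. Size, under stated assumptions.** The documents give neither the frequency of low immunoglobulins in this population nor, after redaction, the size of Part B.
- Assume a reference range covering the central 95%, so 2.5% lie below the lower limit for each of IgG and IgM.
- With full overlap, p = 0.025. With independence, p = 1 − 0.975² = 0.049, or about 0.05.
- Assume n = 20 to 40. The chance of at least one ineligible patient is 1 − (1 − p)ⁿ.

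| n | p = 0.025 | p = 0.05 |
|---|---|---|
| 20 | 1 − 0.975²⁰ = 0.40 | 1 − 0.95²⁰ = 0.64 |
| 40 | 1 − 0.975⁴⁰ = 0.64 | 1 − 0.95⁴⁰ = 0.87 |

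This is the chance of at least one breach of criterion 32. It is not the chance of an infection.

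**The case against.** **Blood tables.** The tabulated count omits screening in every part, so Part B would show 4 with or without a screening draw. That is correct. The tables confirm how the columns line up, but they are not separate evidence that no screening draw exists. That evidence is the two blank cells.

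**Redaction.** The Comments column of the Part B schedules is blacked out, and the 45 mL screening line is not itemized. A hidden note or an unlisted panel could include immunoglobulins. A small doubt remains, but no readable text supports such a draw.

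**Sites could close the gap themselves.** Eligibility is reviewed again predose at V2, local testing is allowed if safety requires it, and an attentive site might query the missing value. These are permissions and do not require the test.

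**Other protections.** Known hypogammaglobulinemia (also in criterion 32) and a history of primary immunodeficiency (criterion 33) are still screened, and Sections 7.1.5 and 7.1.6 set infection and blood-count limits. Later draws would reveal a low value during treatment. This narrows the gap to patients whose low IgG or IgM is unrecognized, and these patients would be found only after exposure.

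**Effect on the safety result.** Part B is randomized against placebo and analyzed descriptively, so ineligible patients can fall in either arm. This stands: the design does not push them toward the active arm. In small groups, however, one such patient can still alter an infection count, and the added risk to that patient is unaffected by the argument.

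**Magnitude.** The probability range rests on an assumed frequency and an assumed n, with no reduction for patients removed by other criteria. That is fair, and the range is illustrative.

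**Conclusion.** The concern holds. As readable, the protocol sets a laboratory exclusion for all parts and omits the test it needs from both Part B schedules. It affects every Part B patient, because none has a scheduled immunoglobulin result before the randomization visit. Under the assumptions above (2.5% to 5% below range, 20 to 40 patients), the chance of dosing at least one patient whom criterion 32 would exclude is 40% to 87%. The contradiction stands without that figure.

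The conclusion assumes that no redacted comment schedules the draw and that a same-visit central result is not available before dosing. The main stake is participant safety in the only part with repeat LY3872386 exposure. Interpretation of the infection data is secondary. It must be fixed before Part B enrolls.

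**What to change.** Mark serum immunoglobulins at V1 in Sections 1.3.2.1 and 1.3.2.2, as Parts A and C already do, so that IgG and IgM are reviewed before randomization at V2. Keep the V2 draw as baseline and mark it P so that it is clearly predose. Screening may run up to 35 days before Day 1 (Section 4.1), which leaves time for a central result.

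The cost is one cell in each of two schedules and one assay per screened patient, with no added visit. Extra blood is probably not needed: the screening line is 45 mL in every part, and in Parts A and C it must already include immunoglobulins. Because that line is not itemized, the sponsor should confirm this. If extra volume were needed, the tables' own tube sizes suggest 8 − 4.5 = 3.5 mL. The Part B totals would become 534 + 3.5 = 537.5 mL (still rounding up to 540) and 509 + 3.5 = 512.5 mL (rounding up to 520 instead of 510).

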5.1. Inclusion Criteria

Participants are eligible to be included in the study only if all of the following criteria apply at screening and/or enrollment:

Age

1. Participant must be 18 to 65 years of age inclusive, at the time of signing the informed consent.

Type of Participant and Characteristics

- 2. Overtly healthy for Part A and Part C as determined by medical evaluation, including medical history, physical examination, laboratory tests, and cardiac monitoring (including ECGs).
 - a. To qualify as Japanese for the purpose of this study, the participant must be first-generation Japanese, defined as the participant's biological parents and all of the participant's biological grandparents must be of exclusive Japanese descent, and must have been born in Japan.
 - b. To qualify as Chinese for the purpose of this study, the participant must be, at a minimum, third-generation Chinese, defined as all 4 of the participant's biological grandparents must be of exclusive Chinese descent and born in China.
- 3. Have clinical laboratory test results within the normal reference range for the population or investigative site or results with acceptable abnormalities that are judged to be not clinically significant by the investigator.
- 4. Have venous access sufficient to allow for blood sampling and administration of IP for IV administration as per the protocol.
- 5. Are reliable, willing to make themselves available for the duration of the study, and willing to follow study procedures.

Body Mass Index and Weight

6. Have a body mass index of 18.0 to 32.0 kg/m^2 , inclusive, for Parts A and C, and 18.0 to 38.0 kg/m^2 , inclusive, for Part B.

Sex and Contraceptive/Barrier Requirements

- 7. Male or Female
 - a. Male participants:

- i. Refer to Appendix 4 (Section 10.4) for definitions and additional guidance related to contraception.
- b. Female participants:
 - ii. WNOCBP may participate in this trial. Refer to Section 10.4 for definitions and additional guidance related to contraception.

Informed Consent

8. Are capable of giving signed informed consent as described in Appendix 1 (Section 10.1.3), which includes compliance with the requirements and restrictions listed in the informed consent form (ICF) and in this protocol.

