- 35. use or intend to use herbal, over-the-counter, or prescription medication within 14 days prior to dosing and during the study, other than estrogen/progesterone as a form of hormone replacement therapy and/or oral contraceptives. Certain medications (for example, vitamin supplements or prescription medications) may be permitted at the discretion of the investigator and in agreement with the sponsor.
- 36. Diagnosed with active endoparasitic infections; suspected or at high risk of endoparasitic infection, unless clinical and (if necessary) laboratory assessment have ruled out active infection before randomization.
- 37. History of preexisting glaucoma, severe acne, osteonecrosis, uncontrolled hypertension, or peripheral edema.
- 38. in the opinion of the investigator or sponsor, are unsuitable for inclusion in the study.
- 50. Known history of diabetes.
- 51. Fasting glucose level of ≥126 mg/dL and glycated hemoglobin ≥6.5% and/or taking anti-diabetes medications at screening.
- 52. Known history of osteoporosis.

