5.3.1. Meals and Dietary Restrictions

During the confinement period (where applicable), participants will consume only food and beverages that are provided to them by the CRU staff. Standard meals (for example, breakfast, lunch, dinner, and snack) will be provided to the participants while resident at the CRU.

In Part A (SAD) and Part B (MAD), participants will be required to fast for approximately 4 hours before study intervention administration. Water is permitted. Participants may eat approximately 2 hours postdose. A normal diet may be consumed at all other times during the study.

In Part C (PO QD prednisone), the participants will be fasted overnight (at least 10 hours) prior to dosing and refrain from consuming water from 1-hour predose until 2-hour postdose, excluding the amount of water consumed at dosing. Food is allowed 4 hours postdose. At all other times during the study, participants may consume water ad libitum.

For all outpatient visits in Parts A, B, and C, participants will be required to fast approximately 10 hours before visits that include clinical chemistry testing. Water is permitted.

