5.4. Screen Failures

A screen failure occurs when a participant consents to participate in the clinical study but is not subsequently assigned to the study intervention or enrolled in the study. A participant who is an alternate in a study group/cohort may be enrolled in the next group/cohort if within the screening window or may screen for a subsequent group, unless the participant was a screen fail.

As Part A and Part C are healthy participant-only studies, individuals who do not meet the criteria for participation in this study (screen failure) may not be rescreened, although screening tests such as clinical laboratory tests and vital signs or ECGs may be repeated at the discretion of the investigator. If subjects have minor deviations in screening assessments (for example, vital signs), these may be repeated at the investigator's discretion to confirm eligibility.

As Part B participants are patients with AD, individuals who do not meet the eligibility criteria for participation in this study (screen failure) may not be rescreened until at least 4 weeks after the date of their previous screen failure and at least 2 weeks after resolution of a skin infection, unless the rescreening is for administrative reasons (see below). Blood tests may be repeated at the discretion of the investigator during screening without being considered a screen failure. Participants may be rescreened once. When rescreening is performed, the individual must sign a new ICF and will be assigned a new identification number.

Allowed Rescreening for Administrative Reasons

An individual may be rescreened once for an administrative reason, such as falling out of the screening window because of scheduling conflicts. The sponsor does not need to approve rescreening for administrative reasons. The rescreening can start immediately after the administrative reason has been resolved.

5.5. Criteria for Temporarily Delaying Enrollment/Randomization/ Administration of Study Intervention of a Participant

Not applicable.

6. Study Interventions and Concomitant Therapy

Study intervention is defined as any investigational intervention(s), marketed product(s), placebo, or medical device(s) intended to be administered to or used by a study participant according to the study protocol.

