7.1.6.2. Glucose and HbA1c Values for Permanent Discontinuation

Any of these laboratory results with no other obvious cause in the opinion of the investigator:

- If 2 fasting glucose measures are ≥126 mg/dL
- If 1 fasting glucose measure is \geq 126 mg/dL and glycated hemoglobin level is \geq 6.5% (48 mmol/mol) (ElSayed et al. 2023)

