7.1.6.3. Adrenal Insufficiency Criteria for Permanent Discontinuation in Part B Only

Morning blood cortisol levels of <83 nmol/L, confirmed by a consecutive test conducted within 3 to 5 days of initial value or fail to respond to cosyntropin (or ACTH) assessment within normal limits.

Sponsor should be contacted, and participant may be referred to a health care provider for additional assessments, monitoring and/or management.

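### Criterion 51 excludes on fasting glucose only when HbA1c is also high, so people already at the protocol's own glucose stopping threshold can enter Parts B and C and meet that threshold with unchanged glucose

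*Protocol*

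**What the plan says.** **Entry.** Criterion 51 in Protocol Section 5.2 reads "Fasting glucose level of ≥126 mg/dL and glycated hemoglobin ≥6.5% and/or taking anti-diabetes medications at screening". Criterion 50 excludes only diabetes that is already known. The other barriers carry no glucose number:

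- Inclusion 2 requires overt health, but only for Parts A and C.
- Inclusion 3 accepts normal laboratory results or "results with acceptable abnormalities that are judged to be not clinically significant by the investigator".
- Exclusion 34 covers abnormal screening values that, "in the opinion of the sponsor or investigator, pose an unacceptable risk to the participant if participating in the study".
- Exclusion 38 is a general unsuitability clause.

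**Stopping.** Section 7.1.6.2 lists two triggers for permanent discontinuation. The first is "If 2 fasting glucose measures are ≥126 mg/dL". The second is one such value together with HbA1c of 6.5% or more. Both apply only where the investigator sees no other obvious cause. The section is not limited to one part, whereas the next is headed "Adrenal Insufficiency Criteria for Permanent Discontinuation in Part B Only".

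**Context.** Section 2.3 lists "increased serum glucose" among the potential risks of LY3872386. Section 5.3.1 says that for outpatient visits "participants will be required to fast approximately 10 hours before visits that include clinical chemistry testing", and Part C dosing follows an overnight fast, so the scheduled chemistry draws in Parts B and C are fasting draws.

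**The concern.** The entry rule is looser than the stopping rule on the same analyte at the same cut-off. Two groups without known diabetes or treatment pass every fixed rule:

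1. Fasting glucose repeatedly at or above 126 mg/dL with HbA1c below 6.5%.
2. HbA1c at or above 6.5% with a screening glucose below 126 mg/dL.

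Group 1 is the main problem. These people sit at the level at which the protocol says dosing should end, yet they may start repeat dosing with a product whose payload, or whose comparator, is a glucocorticoid. Amendment b added the criterion because of the risk of serious glucocorticoid effects, so the wording falls short of its purpose.

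There is also a data cost. Laboratory abnormalities feed the dose decisions in Section 6.6.1. In small cohorts, a discontinuation caused by pre-existing glucose can be mistaken for a drug effect. Section 7.1.6.2 asks for no change from baseline and does not say whether pre-dose values count. If they do, screening and baseline readings alone could satisfy it.

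Part A is a single dose, so stopping has no practical effect there. The conflict matters in Parts B and C.

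**Working it through.** The plan gives no figure on this point, so there is none to reproduce. The check has a logical step and an illustration of size.

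**Step 1: logic.** Let G be fasting glucose ≥126 mg/dL, H be HbA1c ≥6.5% and M be anti-diabetes medication. Criterion 51 can be read as (G and H) or M, or as G and (H or M). For an untreated person (M = 0) both readings reduce to G and H:

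| G | H | Excluded by criterion 51 (either reading) | Excluded if any one suffices | Position under 7.1.6.2 if glucose is unchanged |
|---|---|---|---|---|
| no | no | no | no | not met |
| no | yes | **no** | yes | met by one later value ≥126 |
| yes | no | **no** | yes | met by two values ≥126 |
| yes | yes | yes | yes | met |

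The third row is group 1 and the second is group 2. With M = 1 and G = yes, both readings exclude. Group 1 is therefore the only combination with high glucose that passes entry, however the *and/or* is parsed.

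**Step 2: number of draws.** I counted scheduled chemistry draws after the first dose and before the last-dose visit (Section 1.3). The baseline and last-dose draws are left out.

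- Part B, first schedule (1.3.2.1): V3 to V7, so 5.
- Part B, second schedule (1.3.2.2): V3, V4, V6, V7, so 4.
- Part C, 30-day schedule (1.3.3.1): Days 2, 7 and 21 are printed. One further visit lies between the Day 2–13 and Day 15–29 windows named in Appendix 8, hence Day 14. That makes 4.
- Part C, 7-day schedule (1.3.3.2): 3, as the table can be read.

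**Step 3: chance of meeting the numeric trigger with no drug effect.** *Assumptions, not in the documents:* a constant true fasting glucose μ, independent normal readings and a within-person CV of 3–10%.

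p = P(reading ≥126) = 1 − Φ((126 − μ)/(μ × CV))

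Group 1 needs two or more: P = 1 − (1 − p)^n − n p (1 − p)^(n−1).

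Example with μ = 130, CV = 5%, n = 4: (126 − 130)/6.5 = −0.615, so p = 0.731. Then P = 1 − 0.269⁴ − 4 × 0.731 × 0.269³ = 1 − 0.005 − 0.057 = 0.938.

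| μ | CV | p | n = 3 | n = 4 | n = 5 |
|---|---|---|---|---|---|
| 126 | any | 0.500 | 0.500 | 0.688 | 0.813 |
| 130 | 3% | 0.848 | 0.937 | 0.987 | 0.998 |
| 130 | 5% | 0.731 | 0.822 | 0.938 | 0.979 |
| 130 | 8% | 0.650 | 0.718 | 0.873 | 0.946 |
| 130 | 10% | 0.621 | 0.678 | 0.844 | 0.928 |

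Group 2 needs one or more, with HbA1c taken as ≥6.5%: P = 1 − (1 − p)^n. At μ = 120:

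| CV | p | n = 4 | n = 5 |
|---|---|---|---|
| 3% | 0.048 | 0.178 | 0.217 |
| 5% | 0.159 | 0.499 | 0.578 |
| 8% | 0.266 | 0.710 | 0.787 |
| 10% | 0.309 | 0.771 | 0.842 |

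**The case against.** The strongest reply is that judgement covers both ends. Inclusion 3 puts the burden on the investigator to accept an abnormal result, and exclusions 34 and 38 allow refusal. At the stopping end, a documented screening glucose at the same level could count as another obvious cause, so discontinuation is not forced. The probabilities above are therefore chances of meeting the numeric trigger, not of being stopped. That is correct, and they should be read that way.

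It can also be said that entry and stopping rules need not match. Criterion 51 mirrors the second trigger of 7.1.6.2 and, like both triggers, requires two abnormal results. As a design that is coherent, but it leaves the first trigger without a counterpart at entry.

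Two limits on size also stand. In the 7-day Part C schedule the group 1 chance is lower: 50% at 126 mg/dL and 68–94% at 130. For group 2 in Part C, HbA1c is scheduled only at screening, so the second trigger would rest on a pre-dose HbA1c, and the protocol does not say whether that counts.

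The reply does not remove the gap. It leaves a choice between stopping someone whose glucose has not changed and citing known high glucose as the reason to keep giving a glucocorticoid. Neither should depend on site judgement in a first-in-human study.

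**Conclusion.** The concern holds. No fixed rule keeps out an untreated person without known diabetes who has fasting glucose at or above 126 mg/dL and HbA1c below 6.5%. In Parts B and C that person can meet 7.1.6.2 without any change in glucose. This follows from the wording alone and needs no assumption.

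The size for one such person is high: 69% (4 draws) to 81% (5 draws) at a true value of exactly 126, whatever the CV, and 84–99.8% at 130. The figures at 130 depend on the assumed CV, all depend on independent readings around a constant level, and all precede investigator judgement. The number of people affected is unknown. The change should be made because it is a cheap gain in participant safety; the documents do not show that the problem would be frequent.

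**What to change.** 1. Reword criterion 51 so that any one of these excludes: fasting glucose ≥126 mg/dL confirmed by a repeat before the first dose, HbA1c ≥6.5%, or anti-diabetes medication. Section 5.4 already provides for Part B that "Blood tests may be repeated at the discretion of the investigator during screening without being considered a screen failure", and also lets screening laboratory tests be repeated in Parts A and C. In Part B the repeat belongs within screening, because V2 is also the randomization visit.
2. State in 7.1.6.2 that only post-dose glucose values count.
3. For Part C, either add an on-treatment HbA1c or acknowledge that the rule there rests on the two-glucose trigger.

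Requiring confirmation still lets some borderline people through. At 130 mg/dL with a 5% CV, a repeat after a high first value reaches 126 with probability 0.731. Excluding on a single value would close that gap at the price of more screen failures.

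Items 1 and 2 are wording changes to one criterion and one rule. HbA1c and fasting chemistry are already scheduled at screening in every part, so the running cost is the occasional repeat glucose and slightly more screen failures. An added HbA1c in Part C would be one further test.
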